11.4. Vital Signs

Vital sign measurements for the Safety Set will be summarized using descriptive statistics by visit. The change from baseline will also be summarized in the same manner. Unscheduled vital signs assessments will be excluded from the tables.

All vital signs, weight and BMI measurements will be listed in the ITT Set including data collected at any unscheduled assessments.

In principle, any treatment emergent clinically significant change in vital signs will be reported as an AE.

11.5. Electrocardiogram (ECG)

Life Sciences

Business & Decision

Shift tables from baseline to the worst post-baseline results will be provided for the ECG overall interpretation. The following categories will be used: normal, abnormal and not clinically significant, abnormal and clinically significant. The frequencies of ECG overall interpretation by visit as well as the number and percentage of patients who performed the assessment will be also tabulated.

ECG measurements (HR, QT, QTcF, QTcB, PR, RR, and QRS) will be summarized using descriptive statistics by treatment group and visit. The change from baseline will also be summarized in the same manner.12-lead ECGs measurements are obtained in triplicate. Analysis will be performed using the average of the three measurements. In case of one or two measurements are missing the average will be calculated on the bases of the available measurements. Summaries showing the number and percent of patients with outlier values will be presented by treatment.

ECG interval	Categorical outlier criteria
QTcF	Treatment-emergent value of > 450 and ≤ 480 ms when not present at baseline (new onset)
	Treatment-emergent value of > 480 and ≤ 500 ms when not present at baseline (new onset)
	Treatment-emergent value of > 500 ms when not present at baseline (new onset)
	Increase of QTcF from baseline of > 30 and \leq 60 ms
	Increase of QTcF from baseline > 60 ms
PR	Increase of PR from baseline > 25% resulting in PR > 200 ms
QRS	Increase of QRS from baseline > 25% resulting in QRS > 120 ms
HR	Decrease of HR from baseline >25% resulting in HR < 50 bpm
	Increase of HR from baseline >25% resulting in HR > 100 bpm

Outlier values will be identified using the following criteria:

Any treatment emergent clinically significant ECG abnormality will be reported as an AE.

All ECG data will be listed by patient.

11.6. Physical Examination

Any treatment emergent clinically significant physical examination abnormality will be reported as an AE. Physical examination findings will be listed.

The signs and symptoms of edema will be tabulated by visit and treatment.

11.7. ECOG Performance Status

ECOG performance status will be summarized using shift tables from baseline (Screening) to Week 9.

11.8. Overall Survival

Life Sciences

Business & Decision

Overall survival for the two treatment arms will be analyzed descriptively using Kaplan-Meier estimation. Efron method will be implemented for handling ties. Descriptive statistics will be provided as median time to event (and Interquartile Range). A summary of events and censored subjects will be given for each arm (n, %). K-M Plot with the survival curves for the two treatment arms will also be provided.

The difference in survival between anamorelin and placebo, descriptively assessed using a stratified Cox regression analysis (stratified by stratification factors listed in Section 8.4), will be provided as estimate of hazard ratio (HR) and 95%CIs.

Event or censor time in weeks will be calculated as follows:

- Event time (i.e. death) = ([date of death] [Study Treatment Start Date] +1 day)/7
- Event time (i.e. no death) = ([last follow-up contact date [Study Treatment Start Date] +1 day)/7

In this derivation, "Study Treatment Start date" instead of "Randomization date* is used because Overall Survival is considered as Safety variable.

11.9. Tumor Assessments

Change in tumor assessment at the latest CT scan performed during the treatment period compared to CT scan at baseline (overall response categorized into complete response, partial response, stable disease and progressive disease) will be summarized by treatment group with frequencies and percentages.

Baseline CT scan is performed at screening visit or within 28 days of the first dose of study drug.

All patients at all sites will perform CT scans as per standard local practice and responses evaluated according to the RECIST 1.1. Description of target and non-target lesions as well as overall response before randomization (if any) will be provide as listing.

HELSINN

T AN001 Effective Date 25 JUL 2022 Approved Version 2.00

12. APPENDICES

12.1. Missing value imputation process

Imputation of missing values will be performed following:

- the multiple imputation (MI) method for missing data, based on the approach described in literature by Ratitch (1, 2).
- Single imputation method, which is described, case by case, in the process reported below.

Conventions:

- All observed data will be included in any analysis;
- The missing data of the variables being part of the primary efficacy endpoints (body weight, 5-item Anorexia Symptom Subscale score) and the secondary/exploratory efficacy endpoints will be imputed;
- A specific sensitivity analysis for the primary efficacy endpoint "Mean change in body weight from baseline over 12 weeks" will be performed to replace the body weight value of the patients with fluid retention at the date of the assessment. These values will be firstly set to missing and, then, imputed with the imputation approach reported in Section 10.1.3.2.
- No imputation will be performed for survival status and no data will be imputed after patient death.

When a measurement will be missing for patients who are alive, the imputation will depend on the pattern of missingness: **non-monotone** vs. **monotone**:

- In case of non-monotone pattern, missing values may occur in the middle of a subject record (e.g., missed intermediate visit). These are also called "Intermittent missing values".
- In case of a monotone pattern, it is possible to arrange variables so that, for all subjects, missing values are always located in a block at the end of data records (e.g., due to study discontinuation). These are also called "non-Intermittent missing values".

For the definition see also Section 8.8.

12.1.1. Imputation rules

12.1.1.1. Imputation for Intermittent missing values (nonmonotonic missingness)

These values will be imputed with the value obtained by linear interpolation between prior and post values.

12.1.1.2. Imputation rules for Non-intermittent missing values (monotonic missingness)

Imputation rules for non-intermittent missing values are based on a main rule and some exceptions.

The rule and the exceptions will be applied separately for each efficacy parameter.

Main rule

All missing values will be imputed assuming MNAR, specifically by means of the control-based multiple imputation method.

Reason: Most of the patients are expected to have missing values from time of treatment stop. In addition, the patients under study are characterized by poor prognosis and the reasons for treatment discontinuation are expected to be more related to the background disease than to treatment failure. For this reason, it cannot be assumed that the values after the treatment discontinuation would follow the same trend as before discontinuation because the general conditions, with specific exceptions described below, after discontinuation get to worsen. The implementation of the control-based imputation is conservative because it assumes that the deterioration of the patient condition affects mainly the patients in the active treatment group.

Exceptions

- 1. Independent from reason for discontinuation of treatment, if:
 - at least two non-missing post-baseline assessments are available (first assessment = X_1 and last assessment = X_{last}) and,
 - X_{last} $X_1 \ge 0$ and $X_{\text{last}} \ge$ baseline,

then impute all the missing values with the MAR multiple imputation approach including randomised treatment as the covariate.

- 2. If reason for discontinuation of treatment = "Physician decision" or = "Withdrawal by subjects" and:
 - \circ at least two non-missing post-baseline assessments are available (first assessment = X1 and last assessment = X_{last}) and,
 - $\circ \quad X_{\text{last}} \text{ } X_1 \text{ < 0 and } X_{\text{last}} \text{ < baseline,}$

then impute all missing values to the worst value observed for the subject, considering only the on-treatment (post-baseline) timepoints.

Reasons:

Imputation for Exception 1

This exception is applicable for any reason for discontinuation, when the trend reveals an improvement of the efficacy assessments over time, with the last post-baseline assessment (X_{last}) better than both the baseline and the first post-baseline assessment (X₁). Based on these conditions, it is assumed that the decision of stopping the treatment is not related to the treatment itself (since the efficacy parameter was improving over time). Due to the improvement over time, it can also be assumed that

the treatment effect would have been maintained as it was before interruption for the rest of the observation period. For this reason, the missing values after the treatment discontinuation will be imputed with the Missing at Random (MAR) multiple imputation approach including randomized treatment as the covariate. This approach might be slightly optimistic for values missing at visits far from the visit of the last assessment, however this will not impact the primary endpoint that is limited to week 12, considering that at least assessments at week 3 and at week 6 are requested by the rule.

Imputation for Exception 2

Business & Decision

Life Sciences

This exception is limited to the reasons of treatment discontinuation that are most likely related to lack of efficacy of the treatment; the criterion for considering the unknown values as related to lack of efficacy is the negative trend of the observed efficacy assessments over time, as documented by the last post-baseline assessment (X_{last}) worse than the baseline and the first post-baseline assessment (X_1). Based on these conditions, it is assumed that the decision of stopping the treatment can be related to the treatment itself (lack of efficacy). The missing values will be imputed with the worst value observed for the patient considering only the on-treatment (post-baseline) timepoints.

Final revision of the above rules was done at the BDRM and they have been confirmed.

The details of the process are showed in the following steps.

STEP 1: Single/Multiple imputations

- Impute all intermittent missing data
- Create 100 records for each value
- Application of the Main Rule:

Apply MNAR Control-Based imputation on all subjects (placebo and active treatment) with at least one missing assessment.

- MI on all non-intermittent missing

- only placebo patients contribute to the imputation.

Expectation after imputation: only 1 dataset including:

- ANAM and placebo patients without missing data (all assessments observed)
- ANAM and placebo patients with at least 1 missing assessment imputed by the imputation process.

Note: it is theoretically possible that aberrant values are derived because of the imputation. Aberrant values are defined as follows:

- For each item of the questionnaires:
 - a) Imputed value < the lower limit (0)
 - b) Imputed value > the upper limit (4)
- \circ For the body weight:
 - a) Imputed value < the lower limit (30 Kg)
 - b) No upper limit for the Body Weight is fixed.

In the cases (a) the imputed value will be set equal to the lower value.

In the cases (b) the imputed value will be set equal to the upper value.

Unscheduled assessments of body weight and questionnaires are not considered for imputations. These values will be listed only (and have all ANL0XFLs set to blank).

 Application of Exception 1: Apply MAR (as correction to the previous control-based imputation on patients fulfilling Exception 1) *Note: Values to be imputed with MAR need first to be re-set at missing.* A flag before starting with the imputation process should identify the cases where the exception 1 should be applied. Imputed values after MAR imputation should be within the aberrant values described above for the MNAR imputation
 According to Exception 2: Impute worst value at subject level.

A flag before starting with the imputation process should identify the cases where the exception 2 should be applied. Worst value should be calculated before any imputation.

- The imputation process does not distinguish between missing due to treatment discontinuation and death. All imputed assessments after death must be set to missing.

No covariates, apart from treatment arm (as by variable or covariate, as relevant) and baseline value will be included in the MI models.

For each variable, 100 imputed values will replace each missing value.

The following variables will be separately imputed according to the above mentioned single or multiple imputation methods:

- Weight
- 5-IASS
- 4-item Anorexia Concerns Subscale (4-IACS)
- 12-item A/CS domain

Business & Decision

Life Sciences

- FAACT total score
- FACT-G total score
- FAACT TOI
- Functional Assessment of Chronic Illness Therapy-Fatigue (FACIT-F)
- FACIT-F TOI score

The PGIS and the PGIC endpoints and the hunger assessment will not be imputed.

Once the imputation process is complete, the dataset will contain the observed values and the imputed values.

All the values imputed after the intercurrent event death and set to missing, in respect to the "while-alive" principle will be considered as non-responders in the "responder analyses".

The value of the derived endpoints (e.g.: mean change, duration of benefit, change from baseline) will be computed once the imputation datasets are created.

STEP 2: Perform the relevant analyses.

Each of the imputed datasets for primary/secondary/exploratory efficacy endpoints will be analyzed separately using the method declared in the proper section (for instance, the primary efficacy analysis, see Section 10.1.2, will be based on an ANOVA model to compare the two treatment groups, at a Type-I error threshold of 0.05 two-sided).

Each model will provide an estimate of the treatment effect and of the related standard error.

STEP 3: Combine Parameter Estimates.

The pooling of the estimates will be computed using the Rubin rule (1). The pooled effect and the related p-value will be interpreted for the primary (secondary/exploratory) efficacy analyses.

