8.8. Definitions

Baseline

The baseline value for all efficacy analyses is defined as the value collected at Visit 2 (randomization); if this is not available or collected day(s) later as compared to Visit 2, the value collected at screening visit will be used.

For the following assessments, baseline is the value reported at Screening (V1):

- ECOG PS
- HbA1c
- all Urinalysis parameters
- the Patients' Global Impression of Severity (PGIS) scale
- the Patients' Global Impression of Change (PGIC) scale

The baseline value for all safety analyses is defined as the last measurement performed before study drug administration.

Change from Baseline

Any "Change from baseline" variable will be computed as: "variable" at Visit X – Baseline, with X \geq 3 and Baseline defined as above.

Last assessment

Last assessment performed (body weight / 5-IASS) regardless of treatment discontinuation.

Retrieved dropout

Patient who drops the treatment but who continues to be assessed.

Non-monotone pattern of missingness (also called "Intermittent missing values")

Missing values may occur in the middle of a subject record (e.g., missed intermediate visit). It is expected that a value before the missing assessment, and a value after the missing assessment are available.

Monotone pattern of missingness (also called "non-Intermittent missing values")

Missing values are located in a block at the end of data records (e.g., due to study discontinuation).

Study Treatment Start Date

It is the date of the first intake of the study treatment.

End of Treatment (EOT) Date

It is the date declared in the End of Treatment CRF Form. This date will be used in the derivations unless specific adjustments are needed (e.g., for actual exposure derivation).

Last follow-up contact date

It is the date of the last contact for patients alive. It is the date of last follow-up in case of final phone contact (Visit 11 for patients completing the study, before Visit 11 in case of treatment discontinuation), or the date of last performed visit in case of patient lost to follow-up.

It corresponds to the date of death in case a patient died.

Study completion

A patient will be defined as having "completed" the study when the patient completes Visit 11. Termination of the study before performing Visit 11 will be considered as a premature study discontinuation.

Patients who completed 24 weeks treatment

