12.2.1.2. MAR imputation

PROC MI DATA=DATA1 SEED=458122 OUT=DATA2B NIMPUTE=1; BY _IMPUTATION; CLASS TRTPN; VAR TRTPN W_00 W_03 W_06 W_09 W_12 W_15 W_18 W_21 W_24; MONOTONE REGRESSION; RUN;

Note: DATA2B dataset derives from DATA2A (see output dataset from MNAR placebo control-based imputation) after re-setting at missing the assessments as per Exception 1 (see above)

DATA DATAx ; SET DATAx; Where &sel; <<iidentification of the worst value (WORST) for the subject where: At least 2 non-missing: Xlast<X1 Xlast<baseline >> Run: Data Datax2; Set datax; if W 09=. then W 09=WORST; if W 12=. then W 12=WORST; if W 15=. then W 15=WORST; if W 18=. then W 18=WORST; if W 21=. then W 21=WORST; if W 24=. then W 24=WORST; RUN;

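### As literally worded, Exception 2 can be triggered by an off-treatment last value but imputes the worst on-treatment value only, so a retrieved dropout can be imputed above the last observed value or even above baseline

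*SAP*

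**What the plan says.** **Trigger.** Exception 2 (SAP 12.1.1.2) applies when drug was stopped by physician decision or subject withdrawal, when "at least two non-missing post-baseline assessments are available", and when X_last is below both X_1 and baseline. None of these conditions requires the assessments to be on treatment. SAP 8.8 defines the last assessment as: "Last assessment performed (body weight / 5-IASS) regardless of treatment discontinuation".

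**Value imputed.** The rule is: "then impute all missing values to the worst value observed for the subject, considering only the on-treatment (post-baseline) timepoints". The Reasons paragraph for Exception 2 repeats the on-treatment restriction.

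**Rationale.** The Reasons paragraph states that "the criterion for considering the unknown values as related to lack of efficacy is the negative trend of the observed efficacy assessments over time", shown by a last value "worse than the baseline and the first post-baseline assessment".

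**Off-treatment values exist.** SAP 8.8 defines a retrieved dropout as: "Patient who drops the treatment but who continues to be assessed". SAP 12.1 keeps all observed data in every analysis, and SAP 8.2.2 applies treatment policy to drug discontinuation. SAP 8.3.1 reports that few retrieved dropouts were available and gives no count.

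**Other statements of the rule.** The step list in SAP 12.1.1.2 asks only for the subject's worst value. The worst-value code in SAP 12.2.1 marks the identification "of the worst value (WORST) for the subject where: At least 2 non-missing" and shows no on-treatment filter. SAP 12.2 says the code is illustrative.

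**The concern.** The trigger and the imputed value draw on different sets of visits. A visit kept after drug was stopped can supply the fall that puts a patient into Exception 2. That same visit is then left out when the worst value is picked. A rule written to carry forward a poor outcome can therefore assign an unobserved rebound at every later visit at which the patient is alive.

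The rule is applied separately to each imputed parameter. It can reach both co-primary endpoints, the duration-of-benefit and other secondary endpoints, and the Week 15-24 exploratory endpoints.

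**Working it through.** The plan gives no figure for this point, so there is none to reproduce. The check is of the logic, followed by worked cases with invented patient values.

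**1. Inputs from the SAP**
- Trigger: X_last < X_1 and X_last < baseline, using at least two post-baseline values, on or off drug (12.1.1.2, 8.8).
- Imputed value as written: minimum over on-treatment post-baseline visits (12.1.1.2).
- Endpoint: sum of changes from baseline divided by the number of assessments (10.1.1). I use 4 (Weeks 3, 6, 9, 12) and also show 5, in case baseline counts as an assessment.
- Comparators: 1.8 kg for weight and 1.2-1.4 points for 5-IASS (7.2); 158 patients per arm.

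**2. Logic**
- All observed visits on treatment: X_last is in the set, so the imputed minimum is at most X_last. No problem arises.
- One on-treatment visit, then only off-treatment visits: the imputed value is X_1, which the trigger itself makes larger than X_last. The imputed value is always too high.
- No on-treatment post-baseline visit: the set is empty and the rule gives no value.

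**3. Enumeration.** Integer changes from -4 to +4 at each visit. These are counts of patterns, not probabilities for patients.

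| Observed pattern | Triggered | Imputed above X_last | Imputed above baseline |
|---|---|---|---|
| on, off | 26 | 26 | 16 |
| on, off, off | 234 | 234 | 144 |
| on, on, off | 234 | 174 | 64 |
| all on | - | 0 | 0 |

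First row: for X_last = -4, -3, -2, -1 there are 8 + 7 + 6 + 5 = 26 larger values of X_1, and 4 × 4 = 16 of these pairs have X_1 > 0. The second row multiplies by 9 for the free middle visit. In the third row, both on-treatment values exceed X_last in 64 + 49 + 36 + 25 = 174 patterns, and both are positive in 4 × 16 = 64.

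**4. Weight example.** Baseline 50.0 kg; Week 3 on drug 50.5; Week 6 on drug 50.2; drug stopped by physician decision; Week 9 off drug 47.0; Week 12 missing. The trigger is met because 47.0 < 50.5 and 47.0 < 50.0.
- As written, 50.2 is imputed: (0.5 + 0.2 - 3.0 + 0.2)/4 = -0.525 kg.
- Worst of all observed, 47.0 is imputed: (0.5 + 0.2 - 3.0 - 3.0)/4 = -1.325 kg.
- Difference 0.80 kg. With divisor 5 it is -0.42 against -1.06, a difference of 0.64 kg.

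**5. Duration example (threshold 0, linear interpolation, SAP 10.2.1).** Baseline 50 kg, Week 3 on drug 51, Week 6 off drug 48, then missing.
- As written, 51 is imputed at Weeks 9 and 12: 3 + 1 + 1 + 3 = 8 weeks of benefit.
- With 48 imputed: 3 + 1 = 4 weeks.

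**6. 5-IASS example.** Baseline 8, Week 3 on drug 11, Week 6 off drug 5, then missing.
- As written: (3 - 3 + 3 + 3)/4 = +1.5.
- Worst of all observed: (3 - 3 - 3 - 3)/4 = -1.5. Difference 3.0 points.

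**7. Arm level.** The number of affected patients is assumed; the documents give none.
- Weight, if 2-5% of one arm matched step 4: 0.80 × 0.02 = 0.016 kg to 0.80 × 0.05 = 0.04 kg, or 0.9-2.2% of 1.8 kg.
- 5-IASS, if 1 to 10 of 158 patients in one arm matched step 6: 3.0 × 1/158 = 0.02 to 3.0 × 10/158 = 0.19 points, or 1.6-16% of 1.2. The upper end sits badly with the SAP's statement that retrieved dropouts were few.

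**The case against.** **The phrase may not mean what it literally says.** The parenthesis may be a gloss, so that on-treatment simply means after baseline. Protocol 6.3 and 9.4.1 use treatment period for scheduled visits up to Week 24, even for patients who have stopped drug. The step list and the illustrative code carry no on-drug filter. On that reading the imputed value cannot exceed X_last and the problem disappears. This is a fair reading, but the text restricts the set to on-treatment timepoints in two places and SAP 8.8 keeps on-drug and off-drug assessment apart, so the wording needs settling.

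**The rule was written for patients last seen on drug.** The rationale ties the decline to the decision to stop, which a later visit cannot inform, and SAP 12.1.1.2 expects most missing data to begin at treatment stop. This stands for most patients, but the definition in 8.8 admits the others.

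**Stronger readings that the documents do not support.**
- A reader might infer that text and code must produce different data. SAP 12.2 calls the code examples, and the WORST step is a placeholder, so it is not a competing rule.
- A reader might infer that the rule breaks the treatment policy strategy. Observed off-drug values stay in the endpoint (SAP 12.1), so the strain concerns only the imputed visits.
- A reader might infer a bias in favour of anamorelin. The rule applies to both arms, so the direction is not fixed.

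**Safeguards exist.** SAP 10.1.3.1 plans an analysis without the exceptions, and SAP 10.1.4.4 tabulates retrieved dropouts by arm. Both help interpretation, but the primary analysis keeps Exception 2.

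**Conclusion.** The concern holds on the literal wording, for a narrow group. The patient must be a retrieved dropout who stopped for one of the two listed reasons, had a last off-drug value below both X_1 and baseline, and then had missing data while alive. For such a patient the imputed value can exceed X_last and even baseline, contrary to the stated lack-of-efficacy rationale. If no post-baseline visit was on treatment, the rule has no value to impute. The problem does not arise when all observed visits are on treatment, or if the phrase was meant to cover any post-baseline visit.

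The effect is likely to be small: about 0.016-0.04 kg on one arm's mean under the assumed 2-5%, against 1.8 kg, with power for weight put close to 100% in SAP 7.2. The 5-IASS co-primary has less room (78-87% power), but only a handful of patients could be involved. The patient values are invented and the affected share is assumed. This is a low-priority correction to a primary-analysis rule and no evidence that the primary conclusion is at risk.

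**What to change.** In SAP 12.1.1.2, in both the rule and the Reasons paragraph for Exception 2, replace the closing on-treatment qualifier with: *considering all observed post-baseline timepoints, on or off study drug*. Define WORST the same way in SAP 12.2.1.3. The imputed value can then never be better than X_last, and the case with no on-treatment visit is covered.

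The cost is a wording change in two places plus the WORST definition. The illustrative code already fits. Because the SAP says the rules were confirmed at the blinded data review meeting, the change should be documented and made before unblinding. The only analytic consequence is a less favourable imputed value for a few patients, in either arm.
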